### 5.2 Analysis of primary and secondary outcomes

The total number of postnatal transfusions per infant from birth to the end of the follow-up period, the number of postnatal transfusions per infant  $\geq 7$  days (which is at the start of intervention in the treatment group) and the number of days of additional admissions for postnatal erythrocyte transfusions will be compared between both groups using a Mann-Whitney U test. The time from birth to first postnatal transfusion will be compared between both groups using a log rank test and will be displayed using Kaplan-Meier survival curves (in this case transfusion-free survival) by treatment group. The period of follow-up in this study is 90 days and as such the end point for included infants that do not receive transfusions during this period, is 90 days in the survival analysis. The percentage of infants requiring a postnatal transfusion up to 3 months of life will be compared between both groups using a  $\chi^2$  test. The average or median number, depending on shape of distribution, of EPO injections in the treatment arm will be reported, as well as a summary of reasons to discontinue EPO treatment.

A multiple linear regression analysis will be performed to correct the association between treatment assignment and the primary outcome (number of postnatal transfusions). The following potential

confounders identified from previous research [unpublished data] are to be corrected for if, despite randomization, there is a baseline difference between the groups: type of alloimmunization, EPO-levels at birth, number of IUTs and treatment with exchange transfusion. In case of a non-normal distribution of the number of postnatal transfusions per neonate, log transformation will be applied. If the assumptions underlying linear regression are violated, or if the value zero occurs often, a Poisson regression will be fitted. If the number of postnatal transfusions per infant <7 days of life shows a difference between the two groups, a sensitivity analysis will be performed by performing the multiple linear regression analysis (or Poisson regression) with and without the transfusions administered <7 days. This will differentiate between the clinical course of early and late anemia and will evaluate more specifically the effect of EPO treatment, which is started at 7 days of age.

A linear mixed model will be fitted to assess the course of hemoglobin in the treatment and control group which will be graphically depicted. Each infant has repeated weekly hemoglobin measurements as advised in the protocol, but as the frequency of measurements is not mandatory, the data may show missing values at different time points. These missing values are expected to be at random and not completely at random, as it can be anticipated that a measurement is omitted after a previous positive (high) hemoglobin measure which justifies a longer interval between measurements due to the low risk of sudden anemia warranting transfusion. The course of hemoglobin in both groups is expected to have a negative slope after birth due to ongoing hemolysis and a physiological decline of fetal hemoglobin, which will stabilize over the course of several weeks and then show a positive slope as normal physiology recovers or is artificially raised with postnatal transfusions.

To account for the correlation between repeated measurements on the same subject, a random intercept will be included and, if model fit improves, a random slope in the model. The fixed effects will be treatment, time (with a non-linear functional form that will later be determined to match the shape of the expected de- and increase described above) and the interaction treatment\*time. The primary assessment of whether the two groups differ in their hemoglobin course over time will be based on a test on the interaction treatment\*time (a test which will correspond with the most suitable functional form).

[figure not shown]
Throughout the planned analyses, a p-value below 0.05 is regarded as statistically significant. Statistical analysis will be performed using IBM SPSS Statistics 23.0 (Chicago, Illinois, USA).

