## 2. Background

The mainstay of antenatal treatment of fetal anemia due to red cell alloimmunization is (serial) IUT. The mainstay of postnatal treatment in HDFN is (1) intensive phototherapy and, if necessary, exchange transfusion to treat hyperbilirubinemia and prevent kernicterus, and (2) postnatal transfusions to treat anemia. Up to 80% of infants with HDFN treated with IUT require at least one postnatal transfusion for anemia during the first 3 months of life, with a median of two postnatal transfusions involving two hospital admissions per infant. Postnatal anemia can be divided in early (up to 7 days of life) due to ongoing hemolysis and late anemia (7 days - 3 months of age).

Two mechanisms are attributed late anemia: “hypo-regenerative anemia” characterized by depressed erythropoiesis and “late anemia of hemolytic disease” caused by persisting antibodies, destroying young erythrocytes. “Hypo-regenerative anemia” occurs in particular in neonates treated with several IUTs as a result of bone marrow suppression. Other contributing factors for late anemia have been reported such as severity of HDFN, reduced use of exchange transfusions during the neonatal period and reduced survival of transfused red blood cells. Finally, erythropoietin deficiency is also considered as a possible contributing factor to late anemia.

Erythropoietin (EPO) has been increasingly used in full-term and particular in preterm neonates to prevent or reduce neonatal anemia without short or long-term adverse effects. Several small studies and casuistic reports suggest that neonates with HDFN may benefit from treatment with EPO to reduce the risk of delayed anemia and subsequent transfusions. However, other authors found that EPO may be less effective than expected. Due to the lack of evidence, routine use of EPO is currently not recommended. To determine a role for EPO in this group of patients, a well-designed randomized controlled clinical trial of sufficient sample size is required. Potentially, EPO stabilizes the hemoglobin levels of these infants and thus prevents anemia, hospital admissions for

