#### 4.2 Study design

Randomized controlled trial without placebo. Included neonates will be randomized at birth to treatment with EPO (intervention group) or “standard care”, with 1:1 allocation, to be randomized in varying blocks of 4 and 6, no stratification is applied. In the treatment group, EPO (darbepoetin alfa) is administered subcutaneously at a dosage of 10  $\mu\text{g}/\text{kg}$  once a week, starting at approximately day 7, for a period of 8 weeks. Treatment is administered during weekly home visits in the treatment arm after discharge from the LUMC. Concomitant therapy with folate (0.25 mg/day) is given in both groups (standard practice). Concomitant iron therapy is given if ferritin level drops below 75 microg/l (standard practice). Weekly routine measurements of complete blood counts (including hemoglobin level, hematocrit and reticulocyte count) will be performed in both groups (standard practice). EPO is discontinued if hemoglobin level is  $\geq$  13 g/dL after at least 4 weeks of treatment with EPO. In EPO treated infants, blood pressure will be measured for safety reasons at onset of treatment, after four weeks and eight weeks. Monthly measurements of liver enzymes (aspartate aminotransferase (ASAT), alanine aminotransferase (ALAT), gamma-glutamyl transferase ( $\gamma$ GT) and lactate dehydrogenase (LDH)) will also be performed in all groups (standard practice). In addition, the neonatal EPO-level will be determined at birth in both groups. The number of postnatal transfusions received during the first 3 months of life and hemoglobin levels prior to the postnatal transfusion are recorded. After initial discharge from the LUMC, postnatal transfusions are recommended to be performed when hemoglobin levels fall below aforementioned cut-off values of hemoglobin.

Because of these clearly defined guideline and hemoglobin measures, blinding of caregivers to treatment allocation and use of a placebo was not deemed necessary.

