4.4 Sample size calculation

Based on the (scarce) results in the literature, we expect a 50% reduction in the median number of total postnatal transfusions per patient with EPO treatment, from a median of 2 to 1. For sample size calculation we hypothesized a shift in the distribution of number of transfusions per infant as depicted in Figure 1. The distribution in the 'care as usual' group are based on data from 2000-2014. Based on these expected frequencies, group sample sizes of 21 achieve 81% power to detect a difference of 1.1 between the null hypothesis that both group means are 1.9 and the alternative hypothesis that the mean of the EPO group is 0.8 with estimated group standard deviations of 1.5 and 0.9 and with a significance level (alpha) of 0.05 using a two-sided Mann-Whitney test. The drop-out percentage is estimated at 5%, adding  $(42/0.95 = 44)$  1 infant to each group's sample size.

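### The primary Mann-Whitney test is valid but ignores number of IUTs, a pre-birth factor the SAP itself lists; prespecified rank adjustment would protect against chance imbalance and may gain power

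*SAP*

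**What the plan says.** **Primary test.** Under SAP 5.2 the transfusion counts "will be compared between both groups using a Mann-Whitney U test". Protocol 5.10 names the same test. Neither attaches a covariate to it.

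**Sizing.** SAP 4.4 sizes the trial on that test, at a "significance level (alpha) of 0.05 using a two-sided Mann-Whitney test". It states that "group sample sizes of 21 achieve 81% power to detect a difference of 1.1", with "estimated group standard deviations of 1.5 and 0.9". The target is 44 infants, 22 per arm.

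**Allocation.** SAP 4.2 specifies 1:1 randomization in blocks of 4 and 6, and "no stratification is applied".

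**Number of IUTs.** SAP 2 says that hypo-regenerative late anemia "occurs in particular in neonates treated with several IUTs as a result of bone marrow suppression". SAP 5.2 lists number of IUTs as one of four potential confounders. Protocol 6.1 records it among the maternal and fetal baseline variables, and SAP Table 1 has a row for it.

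**Adjustment.** SAP 5.2 plans a linear regression of the primary outcome, with a log or Poisson fallback. The four factors, which the SAP says were "identified from previous research [unpublished data] are to be corrected for if, despite randomization, there is a baseline difference between the groups", therefore enter only when an imbalance is seen. The SAP does not say how large a difference counts. Protocol 5.10 makes a multivariable model optional and secondary, and its list of factors omits number of IUTs.

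**The concern.** Neither the randomization nor the primary test uses any baseline information, although the SAP points to a relevant factor that is known before every infant is randomized.

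Two things are at stake. If number of IUTs predicts later transfusions, the unadjusted test leaves that variation in the noise and gives up power in a trial that can recruit only about 15 eligible infants a year (SAP 4.1). And with 22 per arm, a sizeable chance difference in number of IUTs is not rare. When one occurs, the primary p-value carries it.

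The planned regression does not remove either problem. It leaves the Mann-Whitney p-value unchanged, and whether it adjusts depends on an undefined judgement about observed balance.

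**Working it through.** **1. The plan's own figure.** Inputs from SAP 4.4: n = 21 per arm, difference 1.1, SDs 1.5 and 0.9, two-sided alpha 0.05.

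- Root-mean-square SD = √((1.5² + 0.9²)/2) = 1.237.
- Normal approximation: 1.1/(1.237 × √(2/21)) = 2.88; 2.88 − 1.96 = 0.92; power 82.2%.
- With the Mann-Whitney efficiency factor 3/π, n becomes 20.05: 1.1/(1.237 × √(2/20.05)) = 2.82; power 80.4%.

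The stated 81% is reproduced without any adjustment. Simulated Mann-Whitney power is somewhat lower, 75-78% at 21 per arm for tied counts with these or similar moments.

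**2. Possible gain, by formula.** If number of IUTs correlates rho with the outcome, adjustment multiplies the residual SD by √(1 − rho²), which is worth a sample-size factor of 1/(1 − rho²). Neither document gives rho, so a range is shown (21 per arm, with 3/π):

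| Assumed rho | Sample-size factor | Power |
|---|---|---|
| 0 | 1.00 | 80.4% |
| 0.2 | 1.04 | 82.0% |
| 0.3 | 1.10 | 83.9% |
| 0.4 | 1.19 | 86.7% |
| 0.5 | 1.33 | 90.2% |
| 0.6 | 1.56 | 94.1% |

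**3. Possible gain, by simulation on tied counts.** Assumed probabilities:

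- Control, 0 to 5 transfusions: 0.20, 0.25, 0.26, 0.11, 0.11, 0.07 (mean 1.89, SD 1.49, median 2).
- EPO, 0 to 3 transfusions: 0.45, 0.35, 0.15, 0.05 (mean 0.80, SD 0.87, median 1).

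These match SAP 4.4. Number of IUTs has five levels with assumed frequencies and is linked to the count through a latent normal correlation. There are 22 infants per arm. The comparison is the tie-corrected Mann-Whitney test against Quade's rank analysis of covariance on number of IUTs.

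| Latent correlation | Mann-Whitney | Rank ANCOVA | Difference (points) |
|---|---|---|---|
| 0 | 76% | 75% | −1 |
| 0.2 | 76% | 77% | +1 |
| 0.3 | 76% | 78% | +2 |
| 0.4 | 76% | 80% | +4 |
| 0.5 | 76% | 83% | +7 |
| 0.6 | 76% | 87% | +11 |

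Overall type I error is 4.7-5.0% for Mann-Whitney and about 5% for rank ANCOVA.

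**4. How often imbalance occurs.** The standardized difference in a baseline variable has standard error √(2/22) = 0.302. P(|difference| > 0.5 SD) = 2 × (1 − Φ(0.5/0.302)) = 2 × (1 − Φ(1.66)) ≈ 10%. For 0.3 SD it is about 32%.

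**5. What imbalance does to the unadjusted test under the null.** For an imbalance of exactly D, the test statistic shifts by rho × D/√(2/22) and its SD becomes √(1 − rho²).

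- D = 0.5, rho = 0.5: shift 0.83, SD 0.866; rejection 9.7%.
- D = 0.5, rho = 0.3: rejection 6.8%.
- D = 0.3, either rho: about 5%.

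Averaged by simulation over all trials with imbalance above 0.5 SD, rejection is about 7-16% for latent correlations 0.3-0.6, against about 4% adjusted. In the other 90% of trials the unadjusted rate is about 3.5-4.7%. The two parts average back to nominal: at correlation 0.6, 0.10 × 16% + 0.90 × 3.5% = 4.75%.

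**The case against.** The strongest reply is that nothing is broken. The Mann-Whitney test is prespecified, holds its level over all randomizations, and is the test on which the trial was sized. Planning and analysis agree. That stands. A reader might infer that the planned test is invalid, or gives the wrong answer in the trial actually run. The documents do not support this: the raised rejection rate applies only to the roughly 10% of randomizations with a large imbalance, and elsewhere the rate is slightly below 5%.

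A reader might also infer that number of IUTs is a strong predictor. That is not supported either. SAP 5.2 calls it a potential confounder and cites unpublished data. SAP 2 ties several IUTs to one of two mechanisms of late anemia, and attributes anemia in the first week to ongoing hemolysis. The primary endpoint counts every transfusion from birth, so the IUT statement covers only part of it. At a correlation of 0.2 to 0.3 the gain is only 1 to 2 points.

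Finally, the planned regression and Table 1 would expose a marked imbalance and could report an adjusted estimate. This is a partial answer. It does not change the primary p-value, the trigger has no threshold, and protocol 5.10 makes the model optional and leaves number of IUTs off its list. A narrower remedy, unconditional adjustment in the regression alone, would repair the estimate but not the primary test.

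**Conclusion.** The point holds as a question of efficiency and robustness. The plan ignores, in its primary test, a baseline factor that it names, already collects, and knows before randomization.

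The size cannot be read from the documents, because it depends on an unstated correlation. Over an assumed latent range of 0 to 0.6, the effect on power runs from a loss of about 1 point to a gain of about 11. Only correlations of 0.4 or more give gains of 4 points or more. Protection against imbalance matters in about one trial in ten. These figures also rest on the assumed count distributions and IUT frequencies. The case for the change is that the possible loss is small and fixed while the possible gain is larger. It should be made, with medium confidence about its size.

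**What to change.** Before database lock and unblinding, which SAP 4.2 places after finalization of the SAP:

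- In SAP 5.2, make the primary test a rank analysis of covariance: rank the transfusion counts, adjust for the rank of number of IUTs, and compare the arms on the adjusted ranks. Apply it whatever balance is observed.
- Keep the unadjusted Mann-Whitney test as a sensitivity analysis.
- Change protocol 5.10 to match, so that the two documents do not name different primary tests.
- In the planned regression, make the adjustment for number of IUTs unconditional, so that an adjusted effect in transfusions per infant is reported. The rank test does not supply one.
- Do not adjust the primary test for exchange transfusion. Infants are randomized at birth and it can occur afterwards.

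If the 2000-2014 data behind SAP 4.4 hold IUT counts, the sponsor could estimate the correlation there first.

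**Cost.** No new data are needed. About 1 power point is lost if number of IUTs is not prognostic, the primary test will differ from the one used for sizing, and a protocol amendment is needed after recruitment has begun.

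### Supportive adjusted model for the transfusion count: covariates enter on an undefined trigger, the log step cannot take zeros, and the Poisson fallback has no dispersion correction (minor point)

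*SAP*

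**What the plan says.** The primary outcome, the number of postnatal transfusions per infant from birth to 3 months, is compared by an unadjusted Mann-Whitney U test (SAP 5.2). The SAP adds a multiple linear regression of the same count on treatment. Four candidate covariates are named: type of alloimmunization, EPO level at birth, number of IUTs, and treatment with exchange transfusion. The rule for entering them is that "confounders identified from previous research [unpublished data] are to be corrected for if, despite randomization, there is a baseline difference between the groups".

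The form of the model can then change twice. First: "In case of a non-normal distribution of the number of postnatal transfusions per neonate, log transformation will be applied". Then: "If the assumptions underlying linear regression are violated, or if the value zero occurs often, a Poisson regression will be fitted". Neither document gives a threshold for these triggers, a way to handle zeros on the log scale, or a scale parameter, robust standard error or overdispersion check for the Poisson model. The sensitivity analysis without transfusions given before day 7 uses the same regression, and runs only if early transfusions differ between the groups, again without a criterion.

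Protocol 5.10 makes a multivariable model optional and secondary, and its covariate list omits number of IUTs. The SAP states that the regression will be performed, and adds IUTs to the list.

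**The concern.** Of the two analyses that SAP 5.2 names for the primary count, only the regression yields a model-based effect estimate. If it is quoted beside the Mann-Whitney p-value, its size and interval should follow from a rule that two statisticians would apply in the same way, and its standard error should fit the data the trial expects.

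Neither is assured. A between-group baseline difference cannot be judged without splitting the data by arm, so the blinding described in SAP 4.2 does not settle the covariate rule. Distribution shape and the share of zeros could be judged on pooled blinded data, but the SAP does not say that they will be. A plain Poisson model assumes that the variance equals the mean, which the SAP's own control inputs contradict.

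Exchange transfusion raises a separate question. The SAP says "Included neonates will be randomized at birth to treatment with EPO", while Protocol 5.6 allows consent during the first week. Exchange transfusion can therefore precede or follow allocation, yet SAP Table 1 treats it as a baseline characteristic.

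**Working it through.** **Inputs.** From SAP 4.4: control mean 1.9, and "the mean of the EPO group is 0.8 with estimated group standard deviations of 1.5 and 0.9"; 21 per arm, raised to 22 for dropout; two-sided alpha 0.05. The Figure 1 frequencies are not visible in the text, so a negative binomial with these means and SDs is assumed.

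**The plan's own figure.** Pooled SD = √[(1.5² + 0.9²)/2] = 1.237. Power with 21 per arm = Φ[1.1/(1.237 × √(2/21)) − 1.96] = Φ(0.92) = 82.2%. Multiplying n by the Mann-Whitney efficiency 3/π gives 80.4%. The stated 81% is reproduced.

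**Zeros.** With k = mean²/(variance − mean), P(0) = [k/(k + mean)]^k.
- Control: k = 3.61/0.35 = 10.3, P(0) = 17.5%, P(0 or 1) = 45.5%, so the median is 2.
- EPO: k = 0.64/0.01 = 64, P(0) = 45.2%, P(0 or 1) = 80.8%, so the median is 1.

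These medians match the SAP's expected change "per patient with EPO treatment, from a median of 2 to 1". The control share is also close to the background statement: "Up to 80% of infants with HDFN treated with IUT require at least one postnatal transfusion", which implies at least about 20% untransfused. Overall (17.5 + 45.2)/2 = 31.3%, or about 14 of 44 infants, would have a zero count. The log of zero is undefined, and zeros would very likely be called frequent, which leads to Poisson.

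**Dispersion (variance/mean).**
- Control: 2.25/1.9 = 1.18. With SD 1.45 to 1.55 and mean 1.95 to 1.85, the range is 1.08 to 1.30.
- EPO: 0.81/0.8 = 1.01.

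**Under no effect** (both arms with the control distribution, 22 per arm):
- Analytic type I error of plain Poisson = 2[1 − Φ(1.96/√1.184)] = 7.2%.
- Simulation gives 6.9% to 7.1%, with 95% CI coverage of about 93.1%. Over the rounding range, type I error is about 5.7% to 8.1%.
- Poisson with Pearson-scaled standard errors and a t reference: 4.8% to 4.9%, coverage about 95.2%.
- Robust HC1 standard errors with a t reference: 4.8% to 5.1%.

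**At the planned effect** (ratio 0.8/1.9 = 0.42; expected transfusions 22 × 1.9 = 41.8 and 22 × 0.8 = 17.6, about 59 in all):
- Poisson SE of the log ratio = √(1/41.8 + 1/17.6) = 0.284.
- True SE = √(1.184/41.8 + 1.0125/17.6) = 0.293.
- Ratio 0.284/0.293 = 0.97, so the SE is about 3% too small; simulated coverage is about 94.8%.
- Nominal power, unadjusted: about 88% for plain Poisson, about 84% with Pearson scaling.

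**Pearson scale below 1.** The estimated scale falls below 1 in about 26% of trials under no effect and about 37% at the planned effect. The SAP would have to say whether that is allowed to shrink the standard error.

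**Covariate trigger.** If number of IUTs is entered only when its baseline p < 0.05 (an assumed reading), with IUTs assumed to explain 0% to 15.5% of control variance, the trigger adds no type I error and changes the significance verdict in under 1% of trials.

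**The case against.** The strongest reply is that little depends on this. The model is supportive, Protocol 5.10 makes it optional, the candidate covariates are listed in advance, and the SAP foresees frequent zeros by naming Poisson. The SAP Table 2 shell has no row for an adjusted estimate, so the regression may not become the headline figure. All of this stands, and it keeps the point minor.

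Four stronger readings are tempting and should be resisted.
- *The covariate trigger inflates the error rate.* The check shows no such effect. The case for a fixed list is reproducibility.
- *The Poisson interval is too narrow in general.* Under the SAP's planning values this holds mainly near no effect; at the planned effect coverage is close to nominal.
- *The log step distorts the effect.* With an added constant of 1, 0.5 or 0.1, a true ratio of 0.42 would appear as 0.64, 0.54 or 0.35. The SAP states no such constant, and its own zero rule would probably bypass the log model. What stands is that the step cannot be carried out as written when zeros occur.
- *The sponsor could pick the most favorable of several fits.* The SAP sets out a sequence, not a free choice, and nothing in it plans selective reporting.

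Pearson scaling is also not the only remedy. Robust standard errors hold the error rate equally well here.

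**Conclusion.** The point holds as a minor one on the supportive adjusted model only. The covariate and model-form triggers are undefined, the log step fails on counts expected to be zero in roughly three infants in ten, and the likely Poisson branch has a type I error of about 7% instead of 5% under no effect. At the planned effect the understatement of the standard error is about 3%.

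This rests on the SAP's rounded means and SDs, on negative binomial counts, and on the null meaning that both arms share the control distribution. If true overdispersion exceeded the planning value, the excess would grow: an assumed dispersion of 1.5 gives 11.0% analytically. Nothing here affects the primary Mann-Whitney test or its stated power.

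**What to change.** In SAP 5.2, delete the baseline-difference trigger and the linear and log steps. Name one supportive model: Poisson regression with log link and dispersion-corrected standard errors, either Pearson-scaled with a t reference on residual degrees of freedom, or robust HC1. Choose one, and if Pearson scaling is used, state whether the scale may fall below 1.

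Always enter treatment and a short fixed list of factors set before randomization. Number of IUTs is a natural candidate, since the SAP says hypo-regenerative anemia "occurs in particular in neonates treated with several IUTs as a result of bone marrow suppression", but the sponsor's unpublished data may support another. With about 59 expected transfusions the list must stay short. Report the rate ratio with its 95% confidence interval beside the Mann-Whitney p-value.

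Use the same model for the sensitivity analysis without transfusions before day 7, and run it unconditionally; otherwise that sentence would refer to a deleted model. Adjust for exchange transfusion only where it preceded randomization, or only in a labelled sensitivity analysis. Align the Protocol 5.10 covariate list with the SAP.

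The change is wording only, since number of IUTs is already recorded (Protocol 6.1). The downside is the fall in this model's nominal power from about 88% to about 84% unadjusted, which is the price of holding 5%. Under assumed prognostic strengths, always entering IUTs costs about 1 point of power if they are not prognostic and gains 1 to 3 points if they are. The documents do not establish which applies.
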